# 6.1.3 Adjuvant treatment

#### Nivolumab

Adjuvant nivolumab should be initiated within 90 days after definitive surgery. Nivolumab will be administered at a flat dose of 480 mg IV every 28 days (every 4 weeks) for one year. We have chosen the 480mg IV dose every 4 weeks in accordance with the application made by Bristol-Myers Squibb to the FDA on July 24, 2017. This dose will be similar to the current FDA approved dose of 240 mg IV every 2 weeks with fewer infusions for the patient.

# 6.2 Nivolumab

# 6.2.1 Dosage Form

Nivolumab Infusion, 100 mg/10 mL (10 mg/mL) is a clear to opalescent, colorless to pale yellow liquid, which may contain light (few) particulates. The drug product is a sterile, non-pyrogenic, single-use, isotonic aqueous solution formulated at 10 mg/mL in sodium citrate, sodium chloride, mannitol, diethylenetriaminepentacetic acid (pentetic acid), and polysorbate 80 (Tween 80), pH 6.0 and includes an overfill to account for vial, needle, and syringe holdup. It is supplied in 10-cc Type I flint glass vials, stoppered with butyl rubber stoppers and sealed with aluminum seals.

#### 6.2.2 Preparation and Administration

Nivolumab is to be administered as an IV infusion through a 0.2-micron to 1.2micronpore size, low-protein binding (polyethersulfone membrane) in-line filter at the protocol specified doses and infusion times. It is not to be administered as an IV push or bolus injection. Nivolumab can be infused undiluted (10 mg/mL) or diluted with 0.9% Sodium Chloride Injection, USP or 5% Dextrose Injection, USP to protein concentrations as low as 0.35 mg/mL. When the dose is fixed (e.g., 240 mg, 360 mg, or 480 mg flat dose), nivolumab can be infused undiluted or diluted so as not to exceed a total infusion volume of 120 mL.

During drug product preparation and handling, vigorous mixing or shaking is to be avoided. Dilution and infusion of nivolumab will be conducted per the package insert for the adjuvant treatment of melanoma. Care must be taken to assure sterility of the prepared solution as the product does not contain any antimicrobial preservative or bacteriostatic agent. Nivolumab infusions are compatible with polyvinyl chloride (PVC) or polyolefin containers and infusion sets, and glass bottles.

# 6.2.3 Storage and Use Conditions

The administration of nivolumab infusion must be completed within 24 hours of preparation. If not used immediately, the infusion solution may be stored under refrigeration conditions (2°C to 8°C, 36°F to 46°F) for up to 24 hours, and a maximum of 8 hours of the total 24 hours can be at room temperature (20°C to

25°C, 68°F to 77°F) and room light. The maximum of 8-hour period under room temperature and room light conditions includes the product administration period.

# 6.3 HF10

#### 6.3.1 Preparation

Preparations of the HF10 product will be provided in vials for injection in aqueous buffer comprised of 20 mmol/L Tris, pH 7.0-7.5, and 10% glycerol. HF10 will be stored at < -70°C. The HF10 product will be diluted with physiological saline just before use to meet the target dose level. Specific instructions will be provided in the Pharmacy Manual.

#### 6.4 **Prohibited Concomitant Medications**

No investigational agents other than the study therapy may be administered. No anticancer therapy other than the study therapy may be administered. Any medication that is considered necessary for the patient's welfare, and that will not interfere with the study medication, may be given at the discretion of the Investigator.

It is recommended that patients who routinely receive warfarin anticoagulant therapy should receive modified anticoagulant treatment with low-molecular-weight heparin (LMWH) during study treatment. Such patients will undergo continued monitoring of coagulation function by PT/INR for the duration of study treatment.

Following are recommendations for providing alternative anticoagulant therapy in warfarin receiving patients during HF10 treatment. However, actual management of anticoagulant therapy in each patient will be at the discretion of the study Investigator and the practice of the treatment center and treating physician.

Patients should be switched from warfarin to low-molecular-weight heparin (LMWH) at least 4 to 5 days prior to HF10 injection.

LMWH treatment should be stopped 24 hours prior to HF10 injection.

LMWH treatment should be reinitiated 24 hours after HF10 injection.

Warfarin should be reinitiated 24 hours after HF10 injection in conjunction with LMWH treatment.

LMWH treatment would then be stopped approximately 3 days later (according to INR monitoring), allowing warfarin approximately 3 days to achieve a therapeutic level of anticoagulation.

Continued INR monitoring is necessary for the duration of study treatment.

Patients should receive anti-viral medication (e.g., acyclovir, famciclovir, or valacyclovir) only in the event of viremia caused by HF10 treatment.

Immunosuppressive agents and immunosuppressive disease of system corticosteroids are also prohibited. Inhaled or topical steroids, and adrenal replacement steroid doses

> 10 mg daily prednisone equivalent, are permitted in the absence of autoimmune disease.

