Nine patients (34.6%) reported HF10-related TEAEs. The most frequent related TEAEs were chills, experienced by 3 patients (11.5%), and fatigue, which was reported for 2 patients (7.7%). Regarding the repeat dosing cohorts, fewer patients (33.3%) in the lower dose cohort (1 x 10^6 TCID50/mL/dose) experienced HF10-related TEAEs compared to patients (50.0%) in the 1 x 10^7 TCID50/mL/dose cohort, suggesting a dose-response. It is notable that the frequent HF10-related TEAEs (chills and fatigue) were generally mild and are symptoms reported commonly and easily managed in viral infections and treatment with other oncolytic viruses. All other HF10-related TEAEs were each reported for one patient. Overall, 8 patients (30.8%) reported severe ( $\geq$  Grade 3) TEAEs. No patients reported an event that was both HF10-related and Grade 3 or greater in severity. No HF10-related allergic events were reported. Also, there were no differences in toxicity between patients who were HSV-1-positive and HSV-1-negative at enrollment. No HF10-related serious adverse events were reported in this study.

Viral clearance was investigated following intratumoral injection of HF10. Viral clearance was assessed in blood, saliva, and urine samples by quantitative polymerase chain reaction (qPCR). Patients showed rapid clearance of virus in blood, saliva, and urine. In both stages of the study, HF10 DNA was not detected in any of the biological samples in the majority of patients. For the few patients in whom HF10 DNA was detected, it was almost exclusively restricted to saliva samples and was only transiently detected in samples. Two patients in Stage 1 had transient virus detection in saliva only. In Stage 2, 6 patients had transient virus detection in saliva only. Two patients in Stage 2 had transient virus detection in blood, and one of these patients also had transient virus detection in urine.

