# **3** POTENTIAL RISKS AND BENEFITS

# 3.1 HF10

Potential risks of investigational intratumoral injections include the following reported adverse events:

Occurring in more than 10% of subjects - chills

Occurring in 1%-10% of subjects - injection site disorders, fatigue, malaise, pyrexia, nausea, dehydration, pruritus, and/or hypotension

One patient with anal and scrotal tumors injected with HF10 experienced swelling in the genital area, skin breakage and scab formation in the area on/near the scrotum.

The results of previous and ongoing clinical trials of HF10 in Japan, and the Phase I clinical trial of HF10 conducted under BB-IND 13,342, suggest that HF10 is safe and tolerable. Few HF10- related adverse events have been reported in any of the trials and are similar across the trials. They include: flu-like symptoms such as fever, chills, fatigue, nausea/vomiting, and hypotension. Such events are consistent both with symptoms of viral infections and adverse events reported in trials of other investigational oncolytic viruses. No HF10-related serious adverse events have been reported in these trials.

In the event that HF10-treated patients experience unexpected viral toxicity, patients may be treated by the anti-herpes drugs acyclovir, famciclovir, or valacyclovir, to which HF10 is sensitive.

The Investigator Brochure may be updated during the course of this study with additional risks and benefits. Please see the current Investigator Brochure for further details about the potential risks and benefits associated with this study.

Treatment with HF10 may offer potential benefits. Preliminary evidence suggests that intratumoral injection with HF10 may result in an antitumor response.

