# 5.2 Exclusion Criteria

Yes/No (Response of "yes" = patient ineligible)

- **5.2.1** Patients with active visceral, central nervous system, or any bone metastases melanoma (Stage IVM1b or IVM1c).
- **5.2.2** Patients whose primary diagnosis was ocular melanoma
- **5.2.3** Patients receiving anti-herpes medication (i.e., acyclovir, famciclovir, or valacyclovir) within 1 week prior to initiating HF10 treatment. Patients may not require intermittent or chronic systemic (intravenous or oral) treatment with an antiherpetic drug other than intermittent topical use.
- **5.2.4** Patients who have an active herpetic skin lesion(s) or prior complications of HSV-1 infection.
- **5.2.5** Uncontrolled intercurrent illness including, but not limited to, ongoing or active infection, symptomatic congestive heart failure, unstable angina pectoris, cardiac arrhythmia, or psychiatric illness/social situations that would limit compliance with study requirements, as determined by the investigator.
- **5.2.6** Medical history of autoimmune disease (e.g. Crohn's disease, ulcerative colitis) or other disease requiring systemic glucocorticoid or immunosuppressive therapy. Subjects who receive daily steroid replacement therapy serve as an exception to this rule. Daily prednisone equivalent at doses up to 10 mg would qualify.
- **5.2.7** Patients with clinically evident Human Immunodeficiency Virus (HIV), Hepatitis B Virus (HBV), Hepatitis C Virus (HCV), or Epstein-Barr Virus (EBV) infection are excluded
- **5.2.8** Pregnant or breast feeding women; women desiring to become pregnant within the timeframe of the study are also excluded.

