#### Table 1: Recommended Dose Modification for Nivolumab
Protocol name: Phase II Neoadjuvant trial of Nivolumab in Combination with HF10 Oncolytic Viral Therapy in Resectable Stage IIIB, IIIc, IVM1a Melanoma (Neo-NivoHF10) Version Date: 22JUL2019 Principal Investigator: [name]

Adverse Reaction	Severity*	Dose Modification
Colitis	Grade 3 diarrhea or colitis	Withhold dose a
	Grade 4 diarrhea or colitis	Permanently discontinue
Pneumonitis	Grade 2 pneumonitis	Withhold dose a
	Grade 3 or 4 pneumonitis	Permanently discontinue
Hepatitis	Grade 2 AST or ALT or total bilirubin increased	Withhold dose a
	Grade 3 or 4 AST or ALT or total bilirubin	Permanently discontinue
Hypophysitis	Grade 2 or 3 hypophysitis	Withhold dose a
	Grade 4 hypophysitis	Permanently discontinue
Adrenal Insufficiency	Grade 2 adrenal insufficiency	Withhold dose a
	Grade 3 or 4 adrenal insufficiency	Permanently discontinue
Type 1 Diabetes Mellitus	Grade 3 hyperglycemia	Withhold dose a
	Grade 4 hyperglycemia	Permanently discontinue
Nephritis and Renal Dysfunction	Grade 2 or 3 Serum creatinine	Withhold dose a
	Grade 4 Serum creatinine	Permanently discontinue
Skin	Grade 3 rash or suspected Stevens-Johnson syndrome (SJS) or toxic epidermal necrolysis (TEN)	Withhold dose a
	Grade 4 rash or confirmed SJSor TEN	Permanently discontinue
Encephalitis	New-onset moderate or severe	Withhold dose a

	neurologic signs or symptoms	
	Immune-mediated encephalitis	Permanently discontinue
Other	Other Grade 3 adverse reaction First occurrence Recurrence of same Grade 3 adverse reactions	Withhold dose a Permanently discontinue
	Life-threatening or Grade 4 adverse reaction	Permanently discontinue
	Requirement for 10 mg per day or greater prednisone or equivalent for more than 12 weeks	Permanently discontinue
	Persistent Grade 2 or 3 adverse reactions lasting 12 weeks or longer	Permanently discontinue

\* Toxicity was graded per National Cancer Institute Common Terminology Criteria for

Adverse Events. Version 4.0 (NCI CTCAE v4).

a Resume treatment when adverse reaction returns to Grade 0 or 1.

If nivolumab is withheld for more than 12 weeks, the treatment will be permanently discontinued.

In the event of a nivolumab dose delay, the concurrent HF10 dose will be similarly delayed; the HF10 dose will then be administered on the same day that nivolumab is administered.

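### Section 6.4 bans immunosuppressants and systemic steroids with no exception for immune-mediated events and ties antivirals to HF10 viremia, which is inconsistent with Sections 7.5, 7.1.1 and 3.1

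*Combined protocol and SAP*

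**What the plan says.** **Steroids and immunosuppressants.** Section 6.4 reads: "Immunosuppressive agents and immunosuppressive disease of system corticosteroids are also prohibited". The sentence after it permits inhaled, topical and adrenal-replacement steroids when there is no autoimmune disease. In the available text the replacement limit appears as more than 10 mg/day prednisone equivalent. Earlier in Section 6.4 a general clause lets the investigator give medication needed for the patient's welfare, provided it does not interfere with the study medication.

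Section 7.5 says that immune-mediated events are managed according to the nivolumab package inserts. The nivolumab dose-modification table in Section 7.1.1 (one of several tables numbered 1) lists as a reason for permanent discontinuation: "Requirement for 10 mg per day or greater prednisone or equivalent for more than 12 weeks". For reactions that lead to a withheld dose, its footnote says: "Resume treatment when adverse reaction returns to Grade 0 or 1". Exclusion 5.2.6 exempts patients on daily steroid replacement: "Daily prednisone equivalent at doses up to 10 mg would qualify".

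**Antivirals.** Section 6.4 says: "Patients should receive anti-viral medication (e.g., acyclovir, famciclovir, or valacyclovir) only in the event of viremia caused by HF10 treatment". Section 3.1 says: "In the event that HF10-treated patients experience unexpected viral toxicity, patients may be treated by the anti-herpes drugs acyclovir, famciclovir, or valacyclovir". Section 2.3.3 describes anti-herpes drugs as rescue therapy for when the virus has to be controlled quickly.

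**The concern.** The prohibited-medication section is where site staff and auditors look to see whether a drug is allowed. Nivolumab is a checkpoint inhibitor, and HF10 is a replication-competent herpes virus. Systemic steroids and anti-herpes drugs are therefore the two rescue treatments most closely tied to the study products. Section 6.4 has no express exception for the first in an immune-mediated event, and it attaches a narrower condition to the second than Section 3.1 does.

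Two things are at stake. A clinician relying on Section 6.4 could hesitate over rescue treatment that other sections allow. And because Section 14.8 counts any departure from the defined treatment plan as a deviation, appropriate treatment of an immune-mediated event could be logged as one.

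**Working it through.** No figure in the plan depends on this point, so the check is mainly a comparison of text.

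**1. Design figures, to confirm they are unaffected.** Inputs from Section 10: 20 evaluable patients, null rate 5%, rejection at 4 or more responses, one-sided alpha 0.05. With X binomial(20, p):
- P(X ≥ 4) at p = 0.05 is 0.0159, the actual type I error.
- P(X ≥ 4) at p = 0.20 is 0.589 (stated: 59%).
- P(X ≥ 4) at p = 0.30 is 0.893 (stated: 89%).

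The stated powers reproduce. None of these inputs involves concomitant medication.

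**2. Steroids: Section 6.4 against Sections 7.5 and 7.1.1.**
- The wording in Section 6.4 is garbled. It may mean all systemic corticosteroids, or (more likely) immunosuppressive doses of them. Neither reading contains an exception for immune-mediated events, and the second has no dose definition.
- The ban on immunosuppressive agents is not garbled and has no exception either.
- Section 7.5 has a rule specific to immune-mediated events, but Section 6.4 does not refer to it.
- The nivolumab table stops treatment when prednisone at 10 mg/day or more is required beyond 12 weeks. That threshold has a purpose only if some patients receive shorter courses and may go on. The footnote then sets recovery to Grade 0 or 1 as the condition for resuming. The conflict with Section 6.4 is by implication, since the table does not itself authorise steroids.

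**3. Antivirals: Section 6.4 against Section 3.1.**
- Section 6.4 requires viremia, attributed to HF10.
- Section 3.1 requires unexpected viral toxicity and says nothing about viremia.
- A patient with suspected local viral toxicity and no demonstrated viremia falls within Section 3.1 and outside Section 6.4.
- Section 7.4 lets exposed healthcare staff be treated with the same drugs if warranted, which is also broader than the rule for patients.

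**4. Does the welfare clause in Section 6.4 settle it?** Not fully. It covers only medication that does not interfere with the study medication. Whether an immunosuppressant interferes with nivolumab, or an anti-herpes drug with HF10, is open to argument. The specific restrictions also come after the general clause and are not made subject to it.

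**5. Replacement-steroid limit.** Section 6.4 shows more than 10 mg/day as permitted; Section 5.2.6 allows up to 10 mg/day. The inequality may be reversed, or it may be an artefact of reading the PDF. It needs checking against the source file, and nothing above depends on it.

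**The case against.** The strongest reply is that the protocol already deals with this. Section 7.5 has a specific rule for immune-mediated events. Section 14.4.1 says that adverse events will be treated appropriately. Section 6.4 opens with the welfare clause. HF10 is delayed whenever nivolumab is, so initial treatment of an immune-mediated event would often fall during a hold. The table row is only a stopping threshold, and the antiviral sentence is worded as a recommendation. On this view what remains is a typing error and a missing cross-reference.

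Much of that stands. It shows what was intended and makes withheld treatment unlikely. It does not make the text consistent: Section 6.4 neither refers to Sections 7.1.1 and 7.5 nor limits its ban to dosing days.

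Three stronger readings are tempting, and the documents do not support them.

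- **Phase I as a measure of the antiviral gap.** In the US Phase I study of 26 treated patients, "Nine patients (34.6%) reported HF10-related TEAEs", and two patients had virus detected in blood. A reader might infer that at least 9 − 2 = 7 of the 9 (77.8%) would have been denied antivirals under Section 6.4 but allowed them under Section 3.1. Nothing shows that any of the nine had unexpected viral toxicity. The frequent related events were chills and fatigue, generally mild, and "No patients reported an event that was both HF10-related and Grade 3 or greater in severity".
- **A steroid rate from the nivolumab Phase 1 study.** A reader might multiply its 14.8% rate of Grade 3-4 drug-related events by 20 and expect about 3 patients to need steroids (0.148 × 20 = 2.96). Those events are not identified as immune-mediated; the listed ones include fatigue and lymphopenia. The share needing steroids is unknown, and Grade 2 events that trigger holds are left out.
- **A viremia trigger that cannot be shown.** The study calendar has no viral test, correlative blood is optional, and the list in Section 13.2 names no viral assay. But that list is not exhaustive, and Section 9.2 allows extra safety evaluations when clinically indicated, so a symptomatic patient can be tested.

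**Conclusion.** The point holds as a low-severity contradiction between safety rules. Section 6.4, read literally, excludes steroids and immunosuppressants for immune-mediated events and antivirals for viral toxicity without viremia, while Sections 7.5, 7.1.1 (by implication) and 3.1 expect or allow them. This is a stated rule that is wrong as worded, which is more than missing detail.

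A reader might go further and conclude that the protocol denies patients rescue treatment. The documents do not support that, given Sections 7.5 and 14.4.1 and the welfare clause. There is no effect on sample size, alpha or power, and no defensible count of affected patients can be drawn from the documents.

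One assumption matters. The conflict with Section 7.5 supposes that the package inserts call for systemic steroids or other immunosuppressants. The inserts are not among the documents, but the prednisone row in the nivolumab table points the same way. The conflict between Sections 6.4 and 3.1 rests on their wording alone.

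**What to change.** In Section 6.4, at the next amendment:

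1. Correct the steroid sentence so that it refers to immunosuppressive agents and immunosuppressive doses of systemic corticosteroids. Add: *except when used to treat immune-mediated adverse events per Sections 7.1.1 and 7.5*.
2. Change the antiviral trigger to *viremia or other suspected HF10 viral toxicity*, in line with Section 3.1.
3. While editing, check the direction of the 10 mg/day replacement-steroid limit against Section 5.2.6 and correct it if it is reversed in the source file.

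The cost is two rewritten sentences and one check. No visit, scheduled test, sample-size or analysis change is needed.

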#### 6.5 **Duration of Therapy**

Subjects must be withdrawn from the study treatment for the following reasons:

- Subject withdraws consent from the study treatment and/or study procedures. A subject must be removed from the trial at his/her own request or at the request of his/her legally acceptable representative. At any time during the trial and without giving reasons, a subject may decline to participate further. The subject will not suffer any disadvantage as a result.
- Adverse events incurred from intra-tumoral administration of the study agent including but not limited to grade 3 or greater persistent infection, delayed healing, necrosis or ulcer formation.
- Subject is lost to follow-up.
- Death.

Subjects may be withdrawn from the study for the following reasons:

- The subject is non-compliant with study drug, trial procedures, or both; including the use of anti-cancer therapy not prescribed by the study protocol.
- If, in the investigator's opinion, continuation of the trial would be harmful to the subject's well-being.
- The development of a second cancer.
- Development of an intercurrent illness or situation which would, in the judgment of the investigator, significantly affect assessments of clinical status and trial endpoints.
- Deterioration of ECOG performance status to 4.

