#### Clinical Studies with HF10 + Ipilimumab in unresectable melanoma

# Phase 2 multicenter trial to evaluate efficacy and safety of HF10 oncolytic virus immunotherapy and ipilimumab in patients with unresectable stage IIIB-IV melanoma in the US (Protocol T14-10682, IND No 13,342)

An ongoing phase 2 trial of HF10 and ipilimumab in unresectable metastatic melanoma patients is assessing whether the antitumor effect of HF10 is enhanced by concurrent ipilimumab treatment. Ipilimumab naïve adults with Stage IIIB, IIIC or IV unresectable melanoma with measurable non-visceral lesion(s) received HF10

injections into single or multiple tumors  $(1 \times 10^7 \text{ TCID}_{50}/\text{mL}, \text{ up to } 5 \text{mL/dose}); 4$ injections every week; then up to 15 injections every 3 weeks. Ipilimumab infusions (3 mg/kg) were given every 3 weeks for 4 doses. Tumor responses were assessed at 12, 18, 24, 36, and 48 wks. Best Overall Response Rate (BORR) was determined at 24 wks. Of 46 pts treated, 20% were stage IIIB, 43% stage IIIC, and 37% stage IV. Most HF10-related AEs were  $\leq$  Grade 2, similar to HF10 monotherapy. No DLTs were reported; 3 Grade 4 AEs reported, all not treatment related. 30.4% had Grade 3 AEs. HF10-related Grade 3 AEs (n=3) were left groin pain, thromboembolic event and lymphedema, hypoglycemia, and diarrhea. Twenty-one (46%) patients had received at least 1 prior therapy for metastatic melanoma. Of 43 efficacy evaluable patients, preliminary BORR at 24 weeks per irRC was 41.8% (11.6% CR, 30.2% PR), disease stability rate 67.4% (25.6% SD). Eight responders (53%) were Stage IV. Overall study BORR, including those after 24 weeks, by irRC was 47.7% (15.9% CR, 31.8% PR), disease stability was 65.9% (18.2% SD). In summary, HF10 in combination with ipilimumab treatment does not appear to exacerbate ipilimumab toxicity, is safe, well tolerated and has both local and systemic antitumor activity. The efficacy appears greater than that seen with ipilimumab monotherapy. Since the clinical trial is on-going, the final results of the trial are still pending.

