# 7.1.2 HF10

In the event that the patient is unable to tolerate HF10 (grade 2 intolerable or higher chills, injection site disorders, fatigue, malaise, pyrexia, nausea, dehydration, pruritus, and/or hypotension which do not respond to optimal management) at the discretion of the treating provider, the dose will be reduced to  $1 \times 10^{6}$  TCID50/mL. The HF10 product will be diluted with physiological saline just before use to meet the target dose level. Specific instructions will be provided in the Pharmacy Manual.

If the patient is unable to tolerate the reduced dose the patient will be withdrawn from treatment.

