All adverse events will be treated appropriately. Such treatment may include changes in study drug treatment as listed in the dose modification section of this protocol (see section 7 for guidance). Once an adverse event is detected, it should be followed until its resolution, and assessment should be made at each visit (or more frequently, if necessary) of any changes in severity, the suspected relationship to the study drug, the interventions required to treat it, and the outcome.

Information about common side effects already known about both Nivolumab and HF10 is described in the Drug Information (section 3) and the most recent investigator brochure. This information will be included in the patient informed consent and will be discussed with the patient during the study as needed.

All adverse events will be immediately recorded in the patient research chart.

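### Sections 6.5 and 7.1.2 give different instructions for the same severe local HF10 reaction (withdraw, or re-inject at a reduced dose), and neither says which prevails

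*Combined protocol and SAP*

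**What the plan says.** **Section 6.5 (Duration of Therapy)** opens a mandatory list: "Subjects must be withdrawn from the study treatment for the following reasons". One entry is adverse events arising from "intra-tumoral administration of the study agent including but not limited to grade 3 or greater persistent infection, delayed healing, necrosis or ulcer formation". A second, discretionary list in 6.5 lets the investigator withdraw a patient if continuing would be harmful.

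**Section 7.1.2 (HF10)** is the only HF10 dose-reduction rule. It applies when the patient cannot tolerate HF10 because of "grade 2 intolerable or higher chills, injection site disorders, fatigue" and several other reactions that do not respond to optimal management. Then, "at the discretion of the treating provider, the dose will be reduced to" 1 x 10^6 TCID50/mL. Withdrawal comes only at the next step: "If the patient is unable to tolerate the reduced dose the patient will be withdrawn from treatment".

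Injection site disorders are not defined. Section 7.1.2 does not mention 6.5, and 6.5 does not mention 7.1.2.

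**The concern.** Necrosis, ulceration, persistent infection or poor healing at an injected lesion is an injection site disorder in the ordinary sense of the term. At grade 3 it meets the 6.5 trigger, and it also lies inside the 7.1.2 range, which starts at intolerable grade 2 and has no top. One section then says stop. The other says continue at a lower concentration and stop only if that fails. The two cannot both be followed.

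What is at stake is the safety of individual patients: a replication-competent virus could be injected again after a serious local reaction for which the protocol elsewhere requires treatment to end. Neoadjuvant injections are 7 to 14 days apart (Section 6.1.1), so the decision is made quickly and at the site.

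**Working it through.** The plan gives no figure on this point. The check is a comparison of text, followed by a rough estimate of how often the conflict could arise.

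**Step 1. Apply both rules to one patient: grade 3 ulcer at an injected lesion, not responding to management.**

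| | Section 6.5 | Section 7.1.2 |
|---|---|---|
| Is the event covered? | Yes, named | Yes, if classed as an injection site disorder |
| Grade range | Grade 3 or above for the named events | Intolerable grade 2 upward, no ceiling |
| Action | Mandatory withdrawal from study treatment | Reduce HF10, at the provider's discretion |
| When withdrawn | At once | Only if the reduced dose is not tolerated |
| Cross-reference | None | None |

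**Step 2. Look for a tie-breaker elsewhere.**
- The graded table in 7.1.1 governs nivolumab.
- The stopping rule in 9.10 needs two subjects with grade 4 or 5 toxicity. It pauses the study and does not direct one patient's dosing.
- The committee review in 14.3 is quarterly, slower than the 7 to 14 day injection interval.
- The harm clause in 6.5 is discretionary.

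None of these sets precedence.

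**Step 3. Frequency.** The input is the phase 2 trial of HF10 plus ipilimumab in Section 2.4: 46 treated patients, same concentration and same 5 mL maximum. It reports that "HF10-related Grade 3 AEs (n=3) were left groin pain, thromboembolic event and lymphedema, hypoglycemia, and diarrhea". The three Grade 4 events there are described as not treatment related. None of the listed related events is persistent infection, delayed healing, necrosis or ulcer, so the count is taken as 0 of 46.

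- One-sided exact 95% upper limit: 1 − 0.05^(1/46) = 6.3%. Over 20 patients: 20 × 0.063 = 1.26.
- Chance of at least one such event in 20 patients, 1 − (1 − p)^20: 18% at an assumed p of 1%, 33% at an assumed 2%, and 73% at the 6.3% limit. The last figure is a ceiling from zero events, not an expectation.
- Adding the 26 treated patients of the US phase I trial (no event both HF10-related and Grade 3 or above): 1 − 0.05^(1/72) = 4.1%, or about 0.8 of 20. Many of those patients had lower or single doses.

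**Step 4. Size of a wider rule, for comparison.** If the n=3 in the sentence quoted in Step 3 counts patients, 3/46 = 6.5% had an HF10-related Grade 3 event of any kind (exact Clopper-Pearson 95% CI 1.4% to 17.9%). Over 20 patients that is 1.3 (0.3 to 3.6).

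**The case against.** The best defence is that the sections reconcile. Section 6.5 is mandatory and names specific serious local events, while 7.1.2 is a general tolerability rule. Staff must follow both, and departing from 6.5 would be a protocol deviation under 14.8. The 7.1.2 list also repeats, in the same order, the commonly reported reactions in Section 3.1, which describes the one case of skin breakage in a separate sentence. That suggests 7.1.2 was written for expected reactions. This is the most sensible reading and it lowers confidence to moderate. It does not close the gap, because 7.1.2 includes an undefined class of injection site disorders, extends upward without limit, and yields nowhere to 6.5.

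Three stronger readings are tempting, and the documents do not support them.

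- **That staff are sent to Section 7 and nowhere else.** Section 14.4.1 says "Such treatment may include changes in study drug treatment as listed in the dose modification section of this protocol (see section 7 for guidance". That wording is permissive. It does not make Section 7 exclusive or displace 6.5.
- **That the nivolumab delay rule pushes patients back to injection.** After a delay, "the HF10 dose will then be administered on the same day that nivolumab is administered". This concerns timing only. Withheld nivolumab resumes once the reaction is Grade 0 or 1, so it gives no support for injecting an active grade 3 lesion.
- **That 6.5 requires withdrawal for injection-related events of any grade.** Its opening words carry no grade. But that reading would leave 7.1.2 nothing to manage among injection-related events, and the grade 3 examples indicate the intended severity.

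**Conclusion.** The inconsistency stands as a minor drafting error in a safety rule, with moderate confidence. For grade 3 or greater persistent infection, delayed healing, necrosis or ulceration from injection, 6.5 requires withdrawal, 7.1.2 can be read to allow reduced-dose re-injection, and no text sets the order.

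The conclusion assumes that these events count as injection site disorders, which is the ordinary meaning of an undefined term. The estimate of rarity assumes that the Section 2.4 list is complete. Those data are preliminary, come from a combination with ipilimumab on a different schedule (4 weekly injections, then up to 15 every 3 weeks, against 9 sessions here), and sit beside one ungraded case of local skin breakage in Section 3.1.

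A reader might infer that the primary endpoint is at risk, because a patient who does not complete the neoadjuvant phase is not evaluable (9.1) and one who discontinues before surgery may be replaced (4.2). With events this rare, the effect on the primary analysis is negligible.

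**What to change.** Add an exception to 7.1.2, directly after the dose-reduction rule, along these lines: *except for persistent infection, delayed healing, necrosis or ulceration of grade 3 or above caused by intratumoral administration; the patient is then withdrawn under Section 6.5 and HF10 is not re-administered.*

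Leave 6.5 unchanged. Rewording it so that every grade 3 or greater event from intratumoral administration forces withdrawal would go too far. Grade 3 pyrexia or fatigue attributed to the injection, which 7.1.2 now manages by reduction, would end treatment. As a rough ceiling that is about 1.3 of 20 patients (Step 4), at a cost in evaluable patients. Some of the events behind that figure, such as hypoglycemia or diarrhea, may not count as events of intratumoral administration.

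The cost of the recommended change is one clause, with no added visits, staff or patients. The treating provider loses the reduced-dose option for the four named events only, and 6.5 already removes it.
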